Healthcare resource utilisation, common mental health problems, and infections in people with inflammatory bowel disease (IBD)

NCT number: Not available at submission

Document date: 6th Dec 2018

Academic contributors

[name], [name], [name] [name]^{3,4}

¹ New Road Surgery, Croxley Green, Hertfordshire, UK

² Department of Gastroenterology, Guy's & St Thomas' Hospital, London, UK.

³ Department of Clinical and Experimental Medicine, University of Surrey, Guildford, United Kingdom

⁴ Royal College of General Practitioners, London, UK

The research is supported by Momentum Data Ltd

Abstract

Background

Ulcerative colitis (UC) and Crohn's disease (CD) are chronic inflammatory conditions collectively termed inflammatory bowel disease (IBD). Both conditions are chronic and involve a lifetime of treatment. Current treatment strategies for IBD focus on the use of immune modulating medications, which have the potential to increase the risk of common infections. An understanding of the healthcare resource utilisation and overall infection risk in IBD is therefore important. Despite increasing treatment options, quality of life is significantly reduced in people with IBD and a high prevalence of mental health disorders has been reported. However, the magnitude of any potential association between IBD and mental illness in adults has not yet been fully explored.

Objective

We aim to provide an accurate and contemporary measurement of the current healthcare resource utilisation in people with IBD. We also aim to provide estimates of infection incidence in this population and the prevalence of common mental health conditions. We will also

Method

We will identify UC and CD using algorithms validated for accurately identifying these conditions from primary care records in the UK. We will identify a prevalent cohort of adults with IBD with the RCGP RSC network over the last decade. We will identify a matched cohort of people without IBD; matched on age, gender and primary care practice. Across these cohorts we will compare healthcare resource utilisation (primary care attendances, number of primary care prescriptions for antidepressant and anxiolytic medications, number of primary care prescriptions for medications used in IBD, recorded secondary care attendances, and issue of statements of fitness for work), incident infections (any common infection, any viral infection, or any gastrointestinal infection), and common mental health conditions (depression, anxiety, and attention deficit hyperactivity disorder).

Lay Summary

Ulcerative colitis and Crohn's disease are the commonest types of inflammatory bowel disease (IBD). Both conditions range in severity from no symptoms to being potentially fatal. Both conditions are treated with medications which suppress the immune system. It is not known whether this increases the risk for infections in these conditions. It is also recognised by healthcare professionals that these conditions cause a considerable amount of psychological distress. However, this has never been measured in a large population sample.

These studies will investigate any associations with treatment and new onset infections. They will also examine the relationship between IBD and common mental health problems (specifically, depression and anxiety) and the impact that these have on the healthcare use (including number of GP appointments, hospital attendances, and medication prescriptions). Combined, these studies should provide a better understanding of the impact of IBD on affected people and provide evidence to support the correct allocation of healthcare resources.

Introduction

Ulcerative colitis (UC) and Crohn's disease (CD) are chronic inflammatory conditions collectively termed inflammatory bowel disease (IBD).¹ In both conditions there is a spectrum of disease ranging from a quiescent state with few or no symptoms to potentially fatal disease. Both conditions commonly require extensive medical intervention over many decades of disease and may also require substantial surgical treatment.^{2, 3} With the global burden of IBD rising, calls have been made for improved treatment options,⁴ and these been met with the development of a range of biologic therapies.¹

Current treatment strategies for UC focus on the use of immune modulating medications. Whilst frequently effective for disease control, these treatments have the potential to increase the risk of common infections,^{5, 6} which includes both common and atypical pathogens.⁶ An understanding of the infection risk in a community-based population with UC is therefore important. However, the existing literature on infection rates in people with UC has focused almost exclusively on secondary care populations. It therefore remains unclear what the total burden of infectious disease is in a population-based cohort with UC and how this compares to those without UC.

Despite increasing treatment options, quality of life is significantly reduced in people with IBD⁷ and the prevalence of mental health disorders has been reported to be higher in children with IBD.⁸ However the magnitude of any potential association between IBD and mental illness in adults has not yet been fully explored.

Given the prolonged course of medical treatment in IBD, it is important for payers to have a good understanding of the total healthcare utilisation of people with IBD. Again, in this area, existing studies have focussed on secondary care based cohorts. Little is known about healthcare resource utilisation in primary care, in people with IBD, in the UK.

Aims

1. We aim to describe the incidence of common infections in a population of individuals with IBD, compared to a matched control population without IBD. We will explore all common infections and also focus on viral and gastrointestinal infections.
2. We will explore how incidence of infection varies by age, and other factors associated with risk of infection in IBD including medication use.
3. We aim to describe the prevalence of common mental health conditions (anxiety, depressive episodes, and recurrent depressive disorder) in people with IBD when compared to an age and gender matched cohort.
4. We aim to explore healthcare utilisation in individuals with IBD with and without common mental health problems.

Methods

Study design

We aim to perform a retrospective matched cohort study. We will match people with UC and CD, to people without IBD. A history of common mental health conditions was assessed at baseline (matching date) in both cohorts, and compared. Both cohorts will be followed-up (retrospectively) from the matching date for incident infections, and healthcare resource utilisation.

Data source

We aim to use the Royal College of General Practitioners (RCGP) Research and Surveillance Centre (RSC) database. This database contains the pseudonymised primary care records of the registered population all from a network of GP practices which provide a representative sample of the UK population.⁹ The RCGP RSC database contains complete data on all events and clinical entities coded in UK primary care. These include demographic information, clinical diagnoses, laboratory test results, primary care issued prescriptions, process of care codes (e.g. specialist referrals), and anthropometric measurements (e.g., body mass index; BMI), and are coded using the Read coding system.¹⁰

UK general practice records provide several advantages for this study type;^{11, 12} UK primary care is a registration-based system (a patient can only register with a single GP), records have been computerised since the 1990s, and pay-for-performance targets (introduced in 2004 through The Quality and Outcomes Framework; QOF) have resulted in consistent high-quality clinical data entry about chronic disease. Studies using the RCGP RSC data have been published across a range of chronic diseases.¹³⁻¹⁵ RCGP RSC practices get feedback on their data quality, including using a dashboard. A particular emphasis of this feedback is “episode typing” – designating cases first, new, or ongoing – which helps differentiate incidence from prevalence.¹⁶

Study population and outcome measures

All adults (aged ≥ 18) registered with a GP practice contributing to the RCGP RCS at the time of data extraction will be eligible for inclusion.

Definition of the IBD cohort

All individuals with one or more diagnostic codes for UC or CD prior to the study start date were eligible for inclusion in the IBD cohort. The use of diagnostic codes to identify IBD from UK primary care records has been validated and shown to be accurate and to correctly differentiate between UC and CD.^{17, 18} The Read codes used to identify UC and CD were based on the codes list used by Abrahami et al.,¹⁸ and mapped to both Read code versions used within the RCGP RSC network (Appendix 1). The use of diagnostic codes to identify IBD has also been shown to have good validity in US claims databases.¹⁹

Definition of the matched cohort

The matched unexposed cohort will be identified by matching individuals with IBD to people without IBD. Matching will be performed on age and gender as a minimum. Follow-up for each matched individual will begin at the same baseline date as those with IBD.

Infections outcomes

Infections outcomes will comprise:

1. The time to first recorded presentation with a new episode of any common infection during the study period; a composite of upper respiratory tract infections, pneumonia, bronchitis, influenza-like illness, skin infections, genital infections, urinary tract infections and gastrointestinal infections.
2. The time to first recorded presentation with a new episode of any viral infection.
3. The time to first recorded presentation with a new episode of any episode of gastrointestinal infection.

The Read codes used to identify infections will be adapted from the validated indicators used in routine surveillance by the RCGP RSC. The chosen infections in the composite infections outcomes were selected principally as they represent the majority of the primary care adult infectious disease burden, and include a mixture of viral, bacterial and fungal infections. First or new episodes of an infection are coded accordingly in the database, enabling differentiation from chronic infections or follow-up visits for the same episode. If available, we will also explore type and pathogens contributing to the incident infections.

Mental health outcomes

The presence of common mental health conditions at baseline will be determined for the case and control cohorts. We will examine three groups of common mental illness as defined by the International Statistical Classification of Diseases and Related Health Problems 10th Revision (ICD10) classification;²⁰ depressive episodes (F32), recurrent depressive disorder (F33), and non-phobia related anxiety disorders (F41). These conditions are chosen as they represent the most common mental health conditions presenting to primary care.²¹ These conditions will be identified using algorithms validated in UK primary care.²² We selected the algorithms used here (Appendix 2) to optimise the positive predictive value. In brief, we will use a concurrent diagnosis and treatment code to identify acute episodes (depressive episodes and anxiety episodes) and for recurrent depression either a historical code for any depression and current treatment or a recurrent

depression specific diagnosis code (Appendix 2). As a secondary analysis we will also explore the prevalence of attention deficit hyperactivity disorder (ADHD) in the case and control cohorts.

Healthcare utilisation outcomes

The components of healthcare utilisation to be examined comprise; number and duration of primary care attendances, number of primary care prescriptions for antidepressant and anxiolytic medications, number of primary care prescriptions for medications used in IBD, recorded secondary care attendances, and issue of statements of fitness for work (also termed fit notes or sick notes).

Antidepressant medication classes to be examined comprise, selective serotonin reuptake inhibitors (SSRIs) and related medications (serotonin and norepinephrine reuptake inhibitors; SNRIs), tricyclic antidepressants (TCAs) and related medications (tetracyclic antidepressant TeCAs), and monoamine oxidase inhibitors (MOAIs). Anxiolytic medications to be examined comprise all benzodiazepines and other related medications indicated for use in anxiety states (Appendix 3). Medications used for the treatment of IBD to be examined will comprise; topical 5-aminosalicylic acid (5-ASA) medications, topical glucocorticoids, oral 5-ASA medications, oral glucocorticoids, non-biologic immunosuppressant medications (cyclosporine, azathioprine, mercaptopurine, methotrexate), and biologic therapies (Appendix 3).

Other baseline measures

Socioeconomic status will be defined using the official national measure; the index of multiple deprivation (IMD).²³ This is calculated at the point of data extraction, using patient postcode, with the resultant scores stratified by deprivation quintile. Ethnicity will be extracted from the primary care record and grouped into major ethnic groups; white, black, Asian, mixed, and others.²⁴ BMI will be defined as the most recently recorded measurement prior to the study start date. Smoking status will be defined using the most recently recorded data prior to the study start date. Diagnosis codes will be used to define the presence of comorbidities at baseline; diabetes, hypertension, atrial fibrillation, angina, myocardial infarction, congestive heart failure, stroke, transient ischaemic attack, chronic kidney disease (stages 3–5), dementia, rheumatoid arthritis, chronic liver disease, asthma and chronic obstructive pulmonary disease (COPD).

Statistical Analyses

Comparison of the prevalence of mental health conditions

We will compare the prevalence of the three common mental health conditions in people with IBD and matched controls prior to the baseline date (January 1, 2015). We will stratify groups by age, and gender, and for those with IBD by condition (UC or CD) and duration of disease, and other important baseline factors. We will evaluate differences in baseline characteristics between the cohorts using the χ^2 test for categorical variables and the unpaired t-test for continuous data. Other statistical tests may be used if appropriate, depending on the data type and distribution.

Comparison of healthcare utilisation

We will compare the measures of healthcare utilisation between people with IBD and matched cohorts over a follow-up period. Follow-up will end at the earliest of; the study end-date (data extraction date), the date of patient transfer from an included practice, or date of death. All individuals contributing at least 1 day of follow-up will be included for analysis. We will stratify and compare healthcare utilisation in people with IBD by age and gender, condition (UC or CD), duration of disease, the presence of mental health conditions, and other important

confounders. All utilisation outcomes will be adjusted for the duration of follow-up and reported as event rates.

Where sample size allows we will examine factors associated with increased healthcare utilisation. We will use regression analyses to assess potential associations between healthcare utilisation outcome measures and important patient and treatment factors.

Comparison of infections

Infection incidence rates will be calculated as the number of events divided by the total person-years of follow-up and expressed as the number per 1000 person-years. We will estimate the risk of infection in people with and without IBD using Cox proportional hazards models, and report estimated hazard ratios for associations with 95% confidence intervals. We will evaluate factors associated with an increased risk of infection. Factors assessed will include age, gender, socioeconomic status, household size (if available), comorbidities, and UC medications.

All statistical analyses will be performed in the R statistical package.

Ethical approval

Study approval will be requested from the Research Committee of the RCGP RSC. The study does not meet the requirements for formal ethics board review as defined using the NHS Health Research Authority research decision tool (<http://www.hra-decisiontools.org.uk/research/>).

Contributors

Research support for this project in several areas including data analysis, literature searching, and medication writing will be provided by Momentum Data. [name] and [name] of Momentum Data have contributed to the writing of this protocol and to the study design. Funding for these studies has been provided by Pfizer UK.

Scientific rigor and study registration

The team ethos at Momentum Data is to support the highest quality research, for patient benefit, with rigorous scientific standards. Publication bias remains an issue in observational studies. Therefore, if approval is granted the protocol will be registered as an observational study with ClinicalTrials.gov and made publicly available prior to the commencement of data analysis. Any protocol amendments will be published alongside this public record of the study and will be noted in any final publication with the rationale for the modification. Any changes will be assessed for the need for ethics approval and further RCGP RSC study approval; these will be sought if required.

References

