SSRIs and related medication	Venlafaxine, Bupropion, Duloxetine, Naltrexone, Citalopram, Dapoxetine, Escitalopram, Fluoxetine, Fluvoxamine, Paroxetine, Sertraline
TCA's	Amitriptyline, Clomipramine, Dosulepin, Doxepin, Mianserin, Trazodone, Trimipramine, Imipramine, Lofepamine, Nortriptyline
MAOIs	Tranlycypromine, Phenelzine, Isocarboxazid, Moclobemide
Anxiolytic medications	Alprazolam, Chlordiazepoxide, Clobazam, Clonazepam, Diazepam, Lorazepam, Oxazepam, Buspirone, Meprobamate, Clomipramine, Clomethiazole
Medication for IBD	
Topical 5-ASA	Mesalazine, Sulfasalazine
Topical glucocorticoids	Budesonide, Hydrocortisone, Prednisolone
Oral 5-ASA	Balsalazide, Mesalazine, Olsalazine, Sulfasalazine
Oral glucocorticoids	Prednisolone, Cortisone, Dexamethasone, Methylprednisolone, Beclomethasone, Betamethasone, Budesonide, Deflazacort
Antimetabolites	Azathioprine, Mercaptopurine, Methotrexate
Biologic therapies	Adalimumab, Golimumab, Infliximab, Vedolizumab

Supplementary table S7. Medications analysed by medication class. SSRI = selective serotonin reuptake inhibitors, TCA = tricyclic antidepressants, MAOI = monoamine oxidase inhibitors, 5ASA = 5-aminosalicylic acid.

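### Drug exposure rests on primary care prescriptions, so any biologic supplied elsewhere would be analysed as no biologic in the infection-by-medication analysis

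*Combined protocol and SAP*

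**What the plan says.** Under Data source, the plan names a single database: "We aim to use the Royal College of General Practitioners (RCGP) Research and Surveillance Centre (RSC) database". It is described as holding "complete data on all events and clinical entities coded in UK primary care", and the drug data listed are "primary care issued prescriptions". No linkage to hospital prescribing, infusion or homecare records is described. Secondary care enters only through recorded attendances.

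Under Healthcare utilisation outcomes, one outcome is the "number of primary care prescriptions for medications used in IBD". The classes to be examined include biologics, which Supplementary table S7 in Appendix 3 gives by drug name only: "Adalimumab, Golimumab, Infliximab, Vedolizumab".

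Aim 2 is to explore infection incidence by age and "other factors associated with risk of infection in IBD including medication use". Under Comparison of infections, the plan states: "Factors assessed will include age, gender, socioeconomic status, household size (if available), comorbidities, and UC medications". It gives no exposure source, time window, reference group or rule for drugs supplied outside the practice.

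**The concern.** Exposure to a drug can be seen only if the practice issued it. Followed as written, the plan would treat a patient whose biologic comes from elsewhere as not taking one. In a biologic contrast that patient joins the reference group. In a contrast for another class, such as glucocorticoids or antimetabolites, the unseen biologic is an unmeasured co-treatment that may confound the estimate.

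The Introduction motivates the infection work by the possibility that immune-modulating drugs raise infection risk, and the Lay Summary says that associations between treatment and new infections will be investigated. A biologic hazard ratio that is close to one, or very imprecise, because exposure was not recorded could be read as reassurance.

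**Working it through.** **Figures in the plan.** The documents give no sample size, event count, biologic prevalence or capture share, so there is no stated figure to reproduce. The numbers below illustrate size under assumptions.

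**Inputs, all assumed.**
- p, the true share of IBD patients on a biologic: 5-15%.
- s, the share of those users who have a primary care prescription: 10-30%.
- HR, the true infection hazard ratio for biologic versus none: 1.5 or 2.0.
- Nobody is falsely recorded as exposed, and captured users have the same infection risk as uncaptured users.

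**Formulas.**
- Treated share of the recorded-unexposed group: q = p(1−s)/(1−ps).
- Observed hazard ratio, approximately: HR/[1+q(HR−1)].
- Inflation of the standard error of the log hazard ratio for a fixed number of events: √{p(1−p)/[ps(1−ps)]}. This follows from a variance of about 1/[D·a(1−a)], where D is the number of events and a is the share recorded as exposed.

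**One case in full (p = 15%, s = 10%).** q = 0.135/0.985 = 0.137. A true 1.5 becomes 1.5/(1+0.137×0.5) = 1.404. A true 2.0 becomes 2.0/1.137 = 1.759. The SE ratio is √(0.1275/0.014775) = 2.94.

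| p | s | Recorded exposed (ps) | q | HR 1.5 seen as | HR 2.0 seen as | SE ratio |
|---|---|---|---|---|---|---|
| 5% | 10% | 0.5% | 4.5% | 1.467 | 1.913 | 3.09 |
| 5% | 30% | 1.5% | 3.6% | 1.474 | 1.931 | 1.79 |
| 15% | 10% | 1.5% | 13.7% | 1.404 | 1.759 | 2.94 |
| 15% | 30% | 4.5% | 11.0% | 1.422 | 1.802 | 1.72 |

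The ranges are therefore q 4-14%, 1.5 seen as 1.40-1.47, 2.0 seen as 1.76-1.93, and an SE ratio of 1.7-3.1.

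**Precision in terms of events.** Take p = 10%, s = 10%, a true HR of 1.5, and a two-sided 5% level to match the planned 95% intervals. Schoenfeld's formula for 80% power is (1.960+0.842)²/[a(1−a)(ln HR)²].
- Full capture: a = 0.10 and HR = 1.5 give 531 events.
- Primary care capture only: a = 0.01 and an observed HR of 1.435 give 6084 events.

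With an assumed 2000 events, power falls from over 99% to 36%.

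Under these assumptions the attenuation is modest. The larger loss is of recorded exposed patients.

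**The case against.** The strongest reply is that the premise lies outside the documents. Nothing in the plan says how biologics are supplied, so the share missed could be small. This stands: every figure above is conditional, and the capture share should be checked before any estimate is interpreted. It does not remove the gap, because the plan has no rule for a user supplied elsewhere, however many there are.

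Second, the infection analysis refers only to UC medications, and no biologic-versus-none contrast is specified. This also stands. That biologics are among those medications, and that exposure comes only from prescriptions, are inferences from the listed classes and the absence of any other source. The data list is not presented as exhaustive, so practice-entered records of hospital drugs are not excluded, but no use of them is planned.

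Third, a reader might infer that the prescription-count outcome is wrong or badly understated. The documents do not support that: its name confines it to primary care prescriptions, and it measures what it says. The remaining risk is interpretive, since the Introduction speaks of payers' interest in total utilisation.

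Fourth, the attenuation formula requires captured users to be representative. If they differ in drug or severity, the direction of bias is unknown and the tabulated hazard ratios do not apply.

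**Conclusion.** The point holds in conditional form. The plan analyses biologics as a medication class and medication use as an infection factor, while the only drug data it describes are issued in primary care. If some biologics are supplied elsewhere, those users are misclassified as untreated in any biologic contrast and are unmeasured co-treatment in the others. Under the assumed ranges, the bias toward one is modest and the loss of precision is substantial. Without representativeness the bias could go either way.

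The scope is limited to Aim 2 and to how biologic prescription counts are read. The IBD-versus-control infection comparison and the mental health prevalence comparison do not use biologic exposure and are unaffected.

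A reader might go further and conclude that biologics must be dropped and that 5-ASA drugs, glucocorticoids and antimetabolites are safe because they are issued in primary care. The documents support neither step: the biologic capture share is unknown, and nothing shows that the other classes are fully captured. Nor do they show that biologics are the class most central to the rationale, which concerns immune-modulating drugs in general.

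**What to change.** 1. Define medication exposure for the infection models, including its source and time window and the classes meant by UC medications.
2. Search the GP record for hospital-medication or other biologic-related entries. Classify the patients found as biologic-exposed, or exclude them from the unexposed reference, and report how many are found. Supplementary table S6 already does something similar for psychological treatment, with codes for counselling by an outside agency and for referrals. Whether usable biologic entries exist is not documented, so the count found is itself informative.
3. Do not interpret a biologic-versus-none hazard ratio based on primary care prescriptions alone. Report captured biologic use descriptively, or give the hazard ratio only with a quantitative bias analysis over stated ranges of prevalence and capture.
4. Label medication results in the infection analysis as primary-care-recorded, state that the same limit may apply to other classes, and note that the biologic prescription count is not total biologic use.

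The cost is protocol wording and one extra code search, plus a bias analysis if the hazard ratio is reported. The downside is a biologic estimate that may be weaker or not reported. The plan commits to registering the protocol before data analysis begins, so the change is best made before then.

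### The eligibility rule is dated to data extraction, the end of follow-up, so age 18 or over and registration are not fixed at the baseline date

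*Combined protocol and SAP*

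**What the plan says.** Under Methods, Study population and outcome measures, adults are eligible if "registered with a GP practice contributing to the RCGP RCS at the time of data extraction will be eligible for inclusion". No other date is attached to the general rule.

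Follow-up starts much earlier. Study design says "Both cohorts will be followed-up (retrospectively) from the matching date for incident infections, and healthcare resource utilisation", and Definition of the matched cohort adds "Follow-up for each matched individual will begin at the same baseline date as those with IBD". The mental health comparison under Statistical Analyses gives the baseline as 1 January 2015.

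Comparison of healthcare utilisation makes the extraction date the study end. Follow-up stops at the earliest of that date, transfer out of an included practice, or death, and anyone with at least one day of follow-up is analysed. Comparison of infections states no censoring rule of its own.

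Four other places touch on entry:
- Definition of the IBD cohort requires a UC or CD code before the study start date, with no condition on age or registration.
- The abstract describes a prevalent cohort of adults with IBD.
- The abstract also says "We will identify a matched cohort of people without IBD; matched on age, gender and primary care practice".
- The Methods promise less on matching: "Matching will be performed on age and gender as a minimum".

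**The concern.** Eligibility for a cohort should be settled by what is known when follow-up starts. Here the only date in the rule is the one on which follow-up ends, and the phrase can qualify either the person's registration or the practice's contribution. The two readings build different cohorts.

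If the person must be registered at extraction, people who died or left the network for good are removed, together with the infections and attendances they had before leaving. Baseline mental health prevalence is then measured only in people still registered years later. If the practice must be contributing at extraction, these people stay in, but nothing explicit says that a participant was 18 or over and registered on the baseline date.

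The choice feeds the infection, utilisation and mental health comparisons. Absolute incidence and prevalence are stated aims, so a shift in level matters even where ratios hold.

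**Working it through.** **Setting the sections side by side**

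1. *Person registered at extraction.* Nobody eligible can have died before extraction. The only transfers left are those of people who rejoined or moved to another network practice. The death and transfer rules in the utilisation section would be almost empty, so this reading conflicts with that section.
2. *Practice contributing at extraction.* The censoring rules work. Age and registration then have no date. Registration at baseline is partly implied by follow-up starting then and by practice matching in the abstract. Adulthood at baseline rests only on the abstract's reference to adults.

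**Time gap**

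The extraction date is not given. Taking it as the date on the title page ("Document date: 6th Dec 2018") is an assumption. From 1 January 2015 that is 1,435 days, and 1,435 / 365.25 = 3.93 years. A person aged exactly 18 at extraction would have been 18 − 3.93 = 14.07 at baseline.

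**Person reading: headcount**

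Share of baseline registrants removed = 1 − exp(−3.93 r), where r is an assumed annual rate of death or transfer. With r = 0.02, 0.05 and 0.10 this gives 7.6%, 17.8% and 32.5%. This is people lost, not bias.

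**Person reading: infection hazard ratio**

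All inputs are assumed. The simulation had 2 million people per arm, time to first infection, an individual hazard ratio of 1.3, control mortality of 0.012 per year, and a gamma frailty of variance 1 acting on both infection and death. Entries are the Cox hazard ratio in the full cohort → in survivors to extraction.

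| Infection rate per year; death multiplier after infection | IBD mortality ratio 1.0 | 1.3 | 1.5 |
|---|---|---|---|
| 0.25; 1 | 1.218 → 1.218 | 1.208 → 1.200 | 1.206 → 1.193 |
| 0.25; 1.5 | 1.213 → 1.214 | 1.211 → 1.197 | 1.210 → 1.188 |
| 0.03; 1 | 1.281 → 1.281 | 1.285 → 1.276 | 1.265 → 1.250 |
| 0.03; 1.5 | 1.280 → 1.280 | 1.272 → 1.256 | 1.265 → 1.240 |

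The largest shift is 1 − 1.240/1.265 = 2.0%. Only comparisons within a pair should be read. Death after infection cannot alter time to first infection, so full-cohort values should agree between multipliers, yet 1.285 and 1.272 differ by about 1% through simulation noise.

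If the frailty acts on infection but not on death, with mortality ratio 1.5 and multiplier 1, the pairs are 1.214 → 1.213 (rate 0.25) and 1.275 → 1.275 (rate 0.03). With multiplier 1.5 the largest shift is about 0.6%.

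**Person reading: absolute infection rates**

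With shared frailty, rates fall by 2.3-4.4% in controls and 2.4-6.4% in IBD. One example is 178.8 to 174.3 per 1,000 person-years in controls: 1 − 174.3/178.8 = 2.5%. With frailty on infection only, the fall is about 0-2%.

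**Person reading: attendances**

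The assumptions are a base rate ratio of 1.3 and attendance raised 3 or 5 times in the last year of life. With equal mortality the ratio does not move materially. The largest shift, at mortality ratio 1.5 and five-fold attendance, is 1.330 → 1.304: 1 − 1.304/1.330 = 2.0%. Control rates fall from 1.024 to 1.003 (2.1%) or from 1.048 to 1.006 (4.0%).

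**Person reading: mental health prevalence**

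Prevalence among those remaining = p·s1 / (p·s1 + (1 − p)·s0), with s = exp(−3.93 × hazard). Assume p = 0.20 in controls and 0.26 in IBD (ratio 1.300), mortality of 0.012 per year, doubled by mental illness.
- Controls: s1 = exp(−3.93 × 0.024) = 0.910 and s0 = exp(−3.93 × 0.012) = 0.954, giving 0.1926.
- IBD with equal mortality: 0.2510, ratio 1.304.
- IBD with mortality ratio 1.5: 0.2466, ratio 1.281, a shift of 1 − 1.281/1.300 = 1.5%.
- If mental illness instead raises all exit (0.072 per year) by 1.3 or 1.5 times, control prevalence becomes 18.7% or 17.8% and the ratio 1.306 or 1.311.

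**The case against.** The strongest reply is that the protocol read as a whole already rules out the person reading. The extraction phrase sits next to the words about the practice contributing, and the utilisation section's censoring would be nearly pointless otherwise. Follow-up starting at baseline, with practice matching in the abstract, implies registration then, and the abstract speaks of adults. Most of the calculated shift therefore belongs to the less likely reading, and much of it comes from letting one frailty drive both infection and death.

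Much of this stands. The practice reading is favoured, and the ratio shifts are small or nil. But the favoured reading does not supply the missing date: registration is implied only in part, and the Methods guarantee matching on age and gender alone. The censoring rule that decides between the readings appears only under utilisation, so the infection section gives an analyst no such guide.

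A reader might infer that the study plans a survivors-only cohort with seriously biased hazard ratios. The documents do not support that: the censoring rule points the other way, and the ratios barely move. A reader might also apply general-population shares of under-18s or late joiners to the practice reading. Those would not describe this cohort, which needs a prior UC or CD code and has age-matched controls.

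**Conclusion.** Wrong as written: the eligibility rule is not anchored to baseline. Severity is minor to moderate.

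The textual finding needs no assumption beyond the baseline preceding extraction, which follows because follow-up runs from one to the other. The true size is unknown. On the assumed inputs, the person reading would shift IBD-versus-control ratios by about 0-2% (hazard ratios by 0-0.6% if frailty for infection does not also drive death) and lower absolute infection rates by about 0-6%. For the practice reading, the documents support no figure for how many people under 18 or not yet registered at baseline would enter.

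Two limits apply. The direct conflict is with the utilisation section; carrying it to infections is an inference. The date 1 January 2015 appears only under the mental health comparison, and the matching date and study start date are not separately dated.

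**What to change.** Reword the eligibility rule so that age 18 or over, and registration with a practice that is in the network at extraction, are both assessed on the baseline (matching) date. Apply it to the IBD and matched cohorts and to all outcomes. State that later death or transfer leads to censoring, not exclusion, and repeat this under Comparison of infections. Confirm whether 1 January 2015 is the baseline for every analysis and whether the matching date and study start date are the same day.

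The cost is a few sentences of protocol text. The extraction must include deceased and deregistered patients; the documents do not confirm that these records are available, so the sponsor should check before analysis. The deprivation score may be missing for some of them, because the protocol says of it "This is calculated at the point of data extraction, using patient postcode".
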